5.2 Sample Size

Sample size estimation was based on effect sizes from Barclay & Barclay (2014) who found that CES reduced subjective anxiety with an effect size of $f = 0.47$. Using GPower, the total sample size was estimated to be 38 to achieve power of 0.80 with an alpha criterion of 0.05. Our goal is therefore 40 complete data sets, with 20 participants in each of the two groups.

6.0 Procedures Involved:

We will use a double-blind, placebo-controlled design with random assignment of participants to one of two experimental groups: Active versus Sham CES. Two versions of the critical learning and virtual reality tasks have been developed (Brunyé & Giles, 2023; used in DEVCOM Armament Center IRB protocol 18-007, Tufts University protocol 1808016), and will be used herein, in balanced order across participants.

Military participants will be transported to and from the CABCS research performance site in Medford, MA, for participating in the baseline and follow-up session. If overnight accommodations are required for Soldiers, those will be provided along with other travel related items (e.g., per diem). Travel will be planned by the research team and coordinated with unit leadership (if troop request) or HRVPO (if HRVs). Civilian participants will not be provided with transportation, accommodations, or any other travel-related compensation.

All non-disposable devices used in the protocol will be disinfected in accordance with Occupational Health and Safety Administration and Centers for Disease Control

guidance, and product label instructions, paying attention to the required personal protective equipment and the contact time needed to achieve disinfection. In addition, all frequently touched surfaces in the research area, such as workstations, countertops, and doorknobs will be cleaned between participants.

Upon scheduling, participants will be randomly assigned to the Active or Sham CES condition, using the [=rand()] function in Microsoft Excel. All participants will complete a Thresholding & Baseline session, the CES administration sessions, and then a Follow-up session.

Testing Day 1: Thresholding & Baseline

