The final testing day will serve as the follow-up session to assess whether 20 sessions of Active (versus Sham) CES will impart any changes to the biochemical, physiological, affective, or behavioral responses to stress induction. This session will be held at approximately the same time of day as the thresholding and baselining session, within 5 days of the last daily CES session. The procedures for this session will precisely match the thresholding and baselining session but without the thresholding phase. After completing the final testing day, participants will have completed the study.

Data Analysis

We will analyze data from our biochemical, physiological, affective, and behavioral measures using Generalized Estimating Equations (GEEs) and/or Analyses of Variance (ANOVAs) to examine changes over the 20 CES sessions, changes from baseline to follow-up, and changes due to Active versus Sham CES. An effect will be deemed statistically significant if the likelihood of its occurrence by chance is $p < 0.05$; to reduce the likelihood of a Type I error, any follow-up comparisons (e.g., t-tests) will use a Bonferroni-corrected alpha criterion.

6.1 Additional Safeguards for Special Populations:

This research is funded by the Department of Defense, and the funding agency is interested in how military personnel respond to CES administration; for that reason, we will prioritize the recruitment of military personnel, and secondarily recruit from civilian populations as required to fulfill our sample size goal.

When recruiting military personnel to participate in this research, we will conform to additional safeguards for the protection of human subjects outlined in DoD Instruction (DoDI) 3216.02. These include additional safeguards to protect participants who may be more vulnerable to coercion or undue influence.

7.0 Investigational Medical Devices:

For the CES sessions, we will be using the Alpha-Stim AID cranial electrotherapy stimulator (CES) medical device, which is an FDA cleared, handheld medical device used for the treatment of anxiety, insomnia, and depression (i.e., AID; see Appendix D).

Because our study is using the device with healthy participants, the device is being used off-label in a manner that is for *investigational use only*. As detailed in the Informed Consent Form, this means that the device is being used in a study examining its safety or effectiveness, and not for the treatment, diagnosis, or prevention of any disorder.

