Cranial Electrotherapy Stimulation on Acute Stress

NCT06034496

May 8, 2025

Statistical Analysis Plan (SAP)

Manipulation Check. To ensure effective stress induction, we will assess AA, HR, CORT, and subjective stress responses to stress exposure during the baseline session. We will compare sampled AA levels from immediately prior to (pre) to immediately after stress exposure (i.e., time points pre and 0-min post-task). We will compare mean HR from immediately prior to (pre) to during stress exposure (i.e., during the RMT, SOT, DMT). We will compare sampled CORT levels from immediately prior to (pre) to 0-minutes after stress exposure (i.e., time points pre and 0-min post-task). We will compare STAI-S scores from immediately prior to (pre) to immediately after stress exposure. For these analyses, we will conduct paired t-tests.

Physiological & Biochemical Responses to CES. To evaluate physiological and biochemical responses to CES, we will use analysis of variance (ANOVA)s to assess the effect of CES Group (2: Active, Sham), Session (2: Baseline, Follow-up), and Time (pre-task, 0-min, 20-min, 40-min, 60-min post-task) on each of six outcome measures: HR, HRV, RR, tonic PD, AA, and CORT (number of levels varies as a function of outcome measure and is described as follows). Each response measure will be assessed in a discretized time series based on its sampling times; continuous measures (e.g., HR) will be discretized into pre-stress versus during-stress time periods. For HR, HRV, respiration, and tonic PD, pre-stress will be calculated as the mean of the one-minute time period immediately preceding the beginning of the tasks, and during-stress will be calculated as the mean of the entire behavioral task performance. For AA and CORT, we will include all five time points in the analysis (i.e., pre-task, 0-min, 20-min, 40-min, 60-min post-task).

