Cognitive & Affective Responses to CES. To evaluate the cognitive and affective responses to CES, we will use mixed ANOVAs to assess the effect of CES Group (2: Active, Sham) and Session (2: Baseline, Follow-up) on each of four cognitive outcome measures, and one affective outcome measure. Cognitive measures include RMT overall accuracy, SOT absolute angular direction error, SOT absolute distance estimate error, DMT discriminability (d'), and DMT response criterion (c). Affective measures include STAI-S scores, and we will use a mixed ANOVA to assess the effect of CES Group (2: Active, Sham), Session (2: Baseline, Follow-up), and Time (pre-task, 0-min, 20-min, 40-min, 60-min post-task).

Mixed ANOVAs will be conducted using package *rstatix* (ver. 0.7.0; Kassambara, 2023) in R (ver. 4.1.2). Mixed ANOVA assumptions will be checked using package *rstatix* (ver. 0.7.0; Kassambara, 2023) in R (ver. 4.1.2). Extreme outliers will be identified, removed, and mean imputed. Normality will be assessed with Shapiro-Wilk Normality Test; non-normal data will be log-transformed. Homogeneity of variance will be assessed with Levene's Test and confirmed all groups had the same or similar variance. Mauchly's test of sphericity will be automatically conducted and corrected for in the mixed ANOVAs analysis.

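### The SAP never uses Baseline as a covariate and does not name the test of CES; for the cognitive outcomes the implied test, change from Baseline, is less precise than Follow-up adjusted for Baseline

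*SAP*

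**What the plan says.** Under the SAP heading Cognitive & Affective Responses to CES, the planned model is: "we will use mixed ANOVAs to assess the effect of CES Group (2: Active, Sham) and Session (2: Baseline, Follow-up"). This applies to every cognitive measure. Five measures are listed, although the text counts four. STAI-S has Time as a third factor.

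Under the SAP heading Physiological & Biochemical Responses to CES, the planned model is: "we will use analysis of variance (ANOVA)s to assess the effect of CES Group (2: Active, Sham), Session (2: Baseline, Follow-up), and Time". Here Time has two levels for HR, HRV, respiration and tonic pupil diameter, and five for alpha amylase and cortisol.

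In all these models Baseline is one level of the outcome factor. The SAP does not mention an interaction and does not say which term answers the question about CES. Protocol section 6.0 (Data Analysis) speaks of changes from Baseline to Follow-up and of changes due to Active versus Sham, by GEE and/or ANOVA. The only covariate in either document is inter-session lag (Protocol section 6.0, The CES Sessions), and the SAP does not carry it forward.

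Protocol section 5.2 bases the sample size on f = 0.47 for subjective anxiety: "the total sample size was estimated to be 38 to achieve power of 0.80 with an alpha criterion of 0.05". The recruitment target is then set in these words: "Our goal is therefore 40 complete data sets, with 20 participants in each of the two groups". Protocol section 6.0 states that "participants will be randomly assigned to the Active or Sham CES condition, using the [=rand()] function in Microsoft Excel"; it describes no stratification or balancing on Baseline.

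**The concern.** In a 2 x 2 design with one between-person and one within-person factor, the Group x Session F test is the square of a two-sample t test on Follow-up minus Baseline. That test subtracts Baseline with weight 1 whatever r is. ANCOVA estimates the weight from the data. When r is well below 1, a weight of 1 adds Baseline noise to the comparison, and it over-corrects any Baseline difference that arose by chance.

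The Baseline outcomes are collected before any allocated CES session, and the thresholding that precedes them uses the same always-active device for everyone. Baseline is therefore a legitimate covariate and is already in the data. At stake are power and interval width in a trial of 40 people, and a CES test that the reader now has to infer.

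**Working it through.** **Inputs.** From Protocol section 5.2: f = 0.47, so d = 2 x 0.47 = 0.94 for two equal groups; alpha 0.05; 20 per arm. Assumed here: d = 0.94 applies at Follow-up; equal SDs at both sessions; a common slope; r from 0.3 to 0.9. The documents do not give r.

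**1. The plan's own figure.** One-way ANOVA with two groups, noncentrality f² x N, df 1 and N-2. N = 38 gives 0.2209 x 38 = 8.39 and power 0.805. N = 36 gives 0.782 and N = 40 gives 0.826. The stated 38 is reproduced as a plain two-group comparison, in which r plays no part.

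**2. Which term tests CES.** If the Group main effect were used, it would average Follow-up with a Baseline that CES cannot have affected. The effect halves to 0.47 SD with variance factor (1+r)/2, and power is 0.44, 0.39 and 0.35 at r = 0.3, 0.5 and 0.7. Group x Session is the sensible reading, but it is an inference.

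**3. Precision for the 2 x 2 cognitive models.** Variance factors, in units of the outcome variance:

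- Change: 2(1-r), df 38.
- ANCOVA: 1-r², times 1 + 1/(40-4) = 1.028 for estimating the slope, df 37.
- Large-sample ratio: (1-r²)/[2(1-r)] = (1+r)/2.

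Noncentral t parameter = 0.94/√(factor x 2/20). At r = 0.3 this is 0.94/√0.140 = 2.51 for change and 0.94/√0.0935 = 3.07 for ANCOVA.

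| r | (1+r)/2 | Ratio with slope cost | Power, change | Power, ANCOVA | Total N for 80%, change v ANCOVA |
|---|---|---|---|---|---|
| 0.3 | 0.65 | 0.67 | 0.69 | 0.85 | 52 v 36 |
| 0.5 | 0.75 | 0.77 | 0.83 | 0.91 | 38 v 30 |
| 0.7 | 0.85 | 0.87 | 0.96 | 0.98 | 24 v 22 |
| 0.9 | 0.95 | 0.98 | 1.00 | 1.00 | 10 v 12 |

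A Follow-up-only comparison has power 0.83 at any r, so below r = 0.5 the change test does worse than ignoring Baseline. A simulation of 10,000 trials per r gave variance ratios of 0.67, 0.77, 0.88 and 0.97. Both estimators averaged 0.93 to 0.94 against a true 0.94.

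**4. Chance imbalance.** The SD of the Baseline difference is √(2/20) = 0.316 SD units. P(|difference| ≥ 0.4) = 2[1 - Φ(0.4/0.316)] = 0.21. Given a difference D, the change estimate shifts by -(1-r)D. For D = 0.4 the size is 0.28 at r = 0.3, 0.20 at r = 0.5 and 0.12 at r = 0.7. Simulated slopes on D were -0.69, -0.50 and -0.30 for change, and about 0 for ANCOVA.

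**The case against.** The strongest reply is that the planned analysis is valid. Over repeated randomisation the change comparison is unbiased and keeps its alpha. That stands. A reader might infer from the imbalance figures that the Group x Session test is biased or prone to false positives. The documents do not support this: the shift is conditional on the observed Baseline difference and averages out over allocations.

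The size depends on two things the documents do not settle. One is r: at 0.5 the change test already has power 0.83, above the 0.80 target, and at 0.7 the gain is only 0.02. The documents contain no repeatability data, so nothing in them places r at the low end. The other is the scale of f = 0.47. If it describes change rather than Follow-up scores, the change test has power 0.83 whatever r is. The variance ratio does not depend on d, so ANCOVA remains the more precise, but the power figures above would not apply.

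A reader might also extend the loss to every outcome. That is not shown. Heart rate, heart rate variability, respiration, pupil diameter, alpha amylase, cortisol and STAI-S have Time as a third factor. The effect of CES on the stress response is then a three-way term, which for the five-point outcomes is an omnibus test with sphericity correction. The change-score identity does not carry over. Nor is a during-minus-pre score a neutral replacement: if CES lowered a measure equally before and during stress, that score would show nothing, whereas Group x Session in the SAP's model could detect it.

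Finally, ANCOVA does not guarantee an unbiased answer here. Protocol section 3.0 expects 40-50% attrition and withdraws people for CES intolerance, which may differ by arm; section 16.0 destroys the data of those withdrawn. Completers may not be a randomised comparison under either analysis.

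**Conclusion.** The point holds as one of efficiency and clarity, not validity. The SAP does not name the CES test and does not use Baseline as a covariate. For the 2 x 2 cognitive outcomes, the term that appears to be meant is less precise than ANCOVA in large samples for every r below 1. With 20 per arm, after the cost of estimating the slope, ANCOVA has 0.67, 0.77 and 0.87 of the change-score variance at r = 0.3, 0.5 and 0.7, and about the same variance near 0.9. The power gain is 0.16, 0.08 and 0.02 at those three values, given d = 0.94 at Follow-up, equal SDs and a common slope.

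It would go too far to conclude that the trial is underpowered. The change test matches the plan's two-group power at r = 0.5 and exceeds it above that; it falls short only if r is lower, which cannot be judged from the documents. Confidence is high in the direction for the cognitive outcomes and limited in the size. For the three-factor outcomes the structure is the same, but no figure is claimed.

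**What to change.** 1. Name the contrast that tests CES for each outcome.
2. For each cognitive outcome, make the treatment test Follow-up = Group + Baseline, with Baseline on the same scale as the outcome if it is log-transformed. Report the adjusted Active minus Sham difference with its 95% CI.
3. For the physiological, biochemical and STAI-S outcomes, first state whether the target is the level or the stress response. Then model the Follow-up values on Group, and Group x Time, with the matching Baseline-session value or values as covariate. Keep the Follow-up pre-task value as an outcome, not a covariate, because CES may have changed it.
4. The mixed ANOVAs can stay as a description.
5. State that adjustment does not remove bias from arm-related withdrawal among completers.

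The change should be fixed before the device key is opened for analysis. It costs SAP wording, a few lines of R for the cognitive outcomes and one degree of freedom per covariate. The three-factor outcomes also need the decision in step 3. No further data or participants are needed.

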During all subsequent CES sessions, 50 μ A below a participant's stimulation threshold will be used as that participant's individualized CES intensity. For example, if the participant achieves 350 μ A, then all subsequent CES sessions will use a 300 μ A intensity. If the participant never reports any symptom and relation to CES as ≥ 3 , the device will be used at the maximum intensity of 500 μ A. Because this study intends to increase stimulation intensity beyond that of our prior study, any participant who does not achieve an individualized stimulation intensity of at least 250 μ A (i.e., $\geq 300\mu$ A threshold) will be dismissed from the study.

Baselining. Participants who achieve the minimum 300 μ A threshold will then complete a series of criterial learning tasks, then a series of cognitive tests while under threat of torso shock. Prior to, during, and after these phases, participants will provide saliva samples and complete the STAI-S questionnaire. These phases are detailed below:

1. Criterial Learning: Participants will learn and be tested to criterion on a series of experimental stimuli. These include a map of a fictitious virtual city, a list of suspicious items from a *be-on-the-lookout (BOLO)* list, and camouflage patterns or objects (e.g., things that are carried in the hands, such as a rifle, broomstick, pipe, etc) representative of friendly versus enemy forces. Participants will be required to reach a minimum of 80% accuracy on these three criterial learning tasks, and will repeat the study-test sequence until they reach that criterion. We will probe for confidence (e.g., *how confident are you in your answer, on a scale from 1-7?*) and metacognitive ratings (e.g., *how likely are you to be able to point to the theater when standing at the restaurant, on a scale from 1-7?*) after each study trial. See Appendix C for details on these three criterial learning tasks. In our prior study, all participants reached the 80% criterion for all tasks within 3 study-test cycles; this is expected to take about 30-35 minutes. If a participant cannot reach criterion within 5 study-test cycles, they will be dismissed from the study.

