During the cognitive testing, if an incorrect response is provided by participants (e.g., > 45° absolute angular error during the spatial orienting task, incorrectly firing upon a friendly or incorrectly letting an enemy pass during the decision-making test), the system will automatically trigger a torso shock. The shock belt will be set at level 3, which (in our previous studies) participants tend to find uncomfortable and stressful, but not painful. If participants cannot tolerate the shock and ask for it to be disabled, we will pause data collection and give them a 5-minute rest period and ask whether they would like to try it again. If they respond *yes*, we will resume data collection (and repeat this rest-retry procedure as necessary). If they respond *no*, we will ask whether they are willing to be rescheduled and try again on another day; if they respond *no*, we will not reschedule. If they respond *yes*, we will reschedule the participant for another session. If during two consecutive sessions they cannot tolerate the shock, they will be dismissed from the study.

Upon completion of testing, participants will return to the private seating area, where they will complete the additional saliva sampling and STAI-S.

3. Saliva Sampling: Participants will provide saliva samples using the Salivabio Oral Swab (SOS) method from Salimetrics. This sampling method involves participants placing a hygienic absorbent swab under their tongue for 2 minutes, and then placing the swab into a vial. The advantage of the SOS method is that participants can do it entirely independently (opening the swab package, placing the swab under the tongue, removing swab from mouth, placing swab in the vial, closing the vial) and without direct contact from the experimenter. Using this method, saliva samples will be taken immediately prior to Questionnaires, immediately prior to Cognitive Testing Under Stress, immediately following Cognitive Testing Under Stress (accompanied by emotional state questionnaires), and at 20-minutes, 40-minutes, and 60-minutes after. In this manner, we will collect a total of 5 saliva samples during this Baseline session.

After completing this series of saliva samples, questionnaires, and tasks, participants will be briefed on the CES session procedures. Participants will then be released for the day. Overall, we expect the Baseline session to last approximately 3 hours, as detailed in the below example schedule:

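### The SAP removes extreme outliers and fills them with an unspecified mean, apparently before any log, and its only remedy for non-normality cannot be applied to the signed criterion c

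*SAP*

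**What the plan says.** The rules stand in the last paragraph of the SAP, under Cognitive & Affective Responses to CES. On outliers there is one sentence: "Extreme outliers will be identified, removed, and mean imputed". The next sentence applies a Shapiro-Wilk test and adds that "non-normal data will be log-transformed". No cut-off, flagging level (group-by-session cell or arms pooled), choice of mean, adjustment for filled values, other remedy for non-normality or sensitivity analysis is given. The Data Analysis part of Protocol section 6.0 does not mention outliers or transformation.

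The outcomes covered include "SOT absolute angular direction error, SOT absolute distance estimate error", together with d' and the response criterion c from the decision-making task. Protocol section 6.0 (Cognitive Testing Under Stress) gives more than 45 degrees of "absolute angular error during the spatial orienting task" as an example of an incorrect response that triggers a shock. Hypothesis H4 (Protocol section 2.0) includes spatial memory performance. The SAP does not say whether the same rules apply to the analyses "on each of six outcome measures: HR, HRV, RR, tonic PD, AA, and CORT".

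**The concern.** Three things follow if the paragraph is applied as it reads.

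- **Filled means count as data.** A filled value adds little or nothing to the spread but is analysed as an observation. With 20 per arm, the Group x Session test keeps 40 - 2 = 38 degrees of freedom however many values were filled.
- **Removal on the raw scale deletes valid high values.** An absolute error is bounded below at zero, so right skew is plausible. A raw-scale cut-off then removes mostly large values that a log would have brought in. On the SOT scores a large error is poor performance, not measurement failure, and H4 concerns that performance.
- **The log is not available for c.** Criterion c takes both signs. If its normality test fails, the plan prescribes a step that cannot be carried out, and the analyst must improvise: add a constant, drop cases or ignore the rule. The same holds for d' only if performance is near chance.

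What is at stake is the Group x Session test, which carries the treatment comparison. Depending on the flagging level chosen, its error rate may rise or its power may fall, and nothing fixes that choice in advance.

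**Working it through.** **The plan's own figure.** Protocol section 5.2 gives f = 0.47, power 0.80, alpha 0.05 and a total of 38. With a two-group F test and noncentrality f²N: 0.2209 x 36 = 7.95 gives power 0.782; 0.2209 x 38 = 8.39 gives 0.805; 0.2209 x 40 = 8.84 gives 0.826. The 38 reproduces. It is not in dispute; it supports the 20 per arm used below.

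**Simulation inputs.** From the documents: 20 per arm, two sessions, alpha 0.05. Assumed, because the documents give none of it: between-session correlation 0.5, extreme meaning beyond 3 x IQR, Shapiro-Wilk at 5% in each of the four cells with a log if any fails (positive outcomes only), and the distributions. The test is the t-test on change, equal to the 2 x 2 Group x Session F on 1 and 38 df. Order: flag, fill with the mean of the flagging level, test normality, log. Main runs used 20,000 trials per scenario (standard error about 0.15-0.2 points).

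**Type I error, flagging by cell.**

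| Shape | No removal | By cell |
|---|---|---|
| Lognormal, log-SD 0.4 / 0.6 / 0.8 | 4.9%-5.1% | 6.5% / 7.5% / 8.3% |
| Capped at 180 degrees, median 30, same log-SDs | 4.8%-5.3% | 6.6% / 7.4% / 8.9% |
| Capped, median 45 | 4.8%-5.3% | 6.6% / 7.6% / 7.9% |
| Capped, median 60 | 4.8%-5.3% | 6.8% / 7.1% / 6.2% |
| Capped, median 80 | 4.8%-5.3% | 6.0% / 5.5% / 5.4% |
| Normal / t5 / t3 | 4.6%-5.2% | 5.2% / 5.5% / 6.4% |
| Gamma shape 4 / Beta(8,2) | 4.6%-5.2% | 6.2% / 5.8% |

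In the uncapped lognormal rows, 0.7% / 1.5% / 2.5% of values are filled, and 42% / 69% / 86% of trials have at least one fill.

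Milder skew (4,000 trials, standard error about 0.35 points): log-SD 0.2 and 0.3 give 5.8% and 5.8% against 5.3% and 5.3% untouched. Scores that average 10 or 20 trials of absolute error (trial counts assumed) give 5.5% and 5.8% against 5.0% and 4.9%. Stronger skew (4,000 trials): log-SD 1.0 gives 10.2% against 5.2%. Smaller runs scatter around the table: 5.7% to 7.1% at log-SD 0.4, and 8.3% to 8.7% at log-SD 0.8.

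Part of the inflation comes from removal itself. At log-SD 0.8 and 1.0, removing without filling gives 6.9% and 7.8%; filling with the cell mean raises this to 8.7% and 10.2%. Naming the mean would therefore not be enough.

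**Arms pooled within session.** Error stays at 4.6%-5.2% in all eight uncapped shapes. For a true effect of 0.9 latent SD, lognormal power of 0.78-0.79 falls to 0.75 / 0.73 / 0.71. The largest losses (4,000 trials, effect 0.94 SD) were 0.829 - 0.744 = 0.085 at log-SD 1.0 and 0.789 - 0.702 = 0.087 for gamma shape 1. Normal power is unchanged at 0.79; t5 rises from 0.79 to 0.80 and t3 from 0.81 to 0.88.

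**Leaving the level open.** With no true effect, cell and pooled flagging disagree on significance in 2.3% / 3.5% / 4.2% of lognormal trials and 0.4% of normal trials. Taking the more favourable of the two gives 7.0% / 8.2% / 8.9% and 5.3%.

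**Criterion c** (assumed normal, SD 0.4, r = 0.5). P(c ≤ 0) = Φ(-mean/0.4): 50% at mean 0, and Φ(-0.75) = 23% at mean 0.3. Participants with at least one session lacking a log: at mean 0, 1 - [1/4 + arcsin(0.5)/(2π)] = 1 - 0.333 = 67%; at mean 0.3, 35%. Chance that the normality rule is triggered when c is truly normal: about 5% for one test; for four cell tests, 1 - 0.95⁴ = 18.5%, simulated as 19% before the fill step and 17% after.

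**d'** (assumed SD 0.5). Values at or below zero: 16% at mean 0.5, 2% at mean 1.0.

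**The case against.** The strongest reply is that the harm may be small in this trial. The documents give no SD or skew for any outcome, a score averaged over many trials would be only mildly skewed, and Protocol section 2.0 reports very low cognitive performance in the authors' prior study, which points towards the capped, near-floor cases where inflation is about a point or less. This stands as a limit on size, although that passage does not say which task was at floor. It does not supply the missing rule.

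Two elements are inferences. That removal precedes the log rests on sentence order in a list of checks; that filled values keep full degrees of freedom rests on silence. Both are the natural reading, but neither is explicit.

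Criterion c has limited weight: H4 names recognition and spatial memory, not c, the problem arises only if normality fails, and the SAP does not say whether one test or four would be run. The point survives because the prescribed step is impossible when triggered.

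Three stronger readings should be resisted. A reader might infer that the rule always inflates error or always costs power; the normal and t3 results contradict that. A reader might infer from the past-tense clause "confirmed all groups had the same or similar variance" that the data had already been analysed; it may be a drafting slip, it concerns variances, and it says nothing about imputation. Conversely, a reader might take "Participants will be required to reach a minimum of 80% accuracy on these three criterial learning tasks" as assurance that d' will be well above zero; that criterion applies to learning before the virtual-reality test, and the prior study reported low performance on its cognitive tasks.

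**Conclusion.** The point holds in conditional form and should be fixed. The wording is deficient whatever the data look like: the outlier rule is not reproducible, it treats fills as observations, and the only transformation offered cannot be applied to a signed outcome.

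The numerical effect rests on the assumed skew, the 3 x IQR cut-off and 20 per arm. Flagging by cell gives about 5%-6% error for mild skew or near-cap scores and about 7%-9% for moderate to strong skew, with one very skewed case above that. Pooled flagging keeps error near 5% and costs up to about 9 points of power under right skew. There is no material effect for normal data, and a gain in power is possible with heavy tails. For c, 23%-50% of values would have no log under the assumed means and SD, with a 5% to 19% chance of meeting the problem if c is truly normal. Confidence is high on the wording and moderate on size.

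**What to change.** 1. Keep all valid observed values in the primary analysis. Set a value to missing only for a documented measurement failure judged blind to arm, and do not analyse a filled mean as an observation.
2. As a sensitivity analysis, report results without values flagged by one stated cut-off, applied with arms pooled and on the analysis scale.
3. Specify in advance that the two SOT error scores are analysed on the log scale, with a stated rule for any zero. The log comes before any outlier check and is not triggered by Shapiro-Wilk.
4. Analyse c and d' untransformed, with a permutation test on the change score if non-normal.
5. State whether these rules also cover the physiological and biochemical outcomes. If data have already been seen, label the change post hoc.

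Checks on the remedy: keeping all values, with positive outcomes logged unconditionally, gave 4.6%-5.2% error in all eight shapes. With log first and then pooled flagging, only 0.02% of lognormal values were flagged and the effect shrank by 0.1%. The permutation test gave 4.8%-5.6% for normal, t5, t3 and gamma shapes, with the t-test's power (0.78-0.80), so its merit is that it can always be carried out. The log should not be extended to left-skewed scores: on Beta(8,2), log first with cell filling gave 7.3%.

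The cost is SAP wording and standard software, with no new data. The downside is that genuine extremes stay in, which may widen intervals and lower power for heavy-tailed outcomes (t3: 0.81 with all values kept, against 0.88 with pooled filling).
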